PK/PD/Immunogenicity Tests										
PK 		X	X	X	X	X	X	X		
Total and free C5 		X	X	X	X	X	X	X		
Immunogenicity (predose) 		X					X	X		
Biomarker Tests										
Serum and plasma biomarkers (predose) 	X	X	X	X	X	X	X	X		
Other										
Concomitant medication 	X	<<monitor continuously>>								X
Nonpharmacologic treatments and therapies 	X	<<monitor continuously>>								X
Patient-reported Outcomes										
SF-12							X			X
EQ-5D-5L							X			X

. The Day 1 visit may occur on the same day as Screening.

. Patients randomized to ravulizumab + BSC will receive a weight-based dose of ravulizumab on Day 1 (Table 5). On Day 5 and Day 10, additional doses of 600 mg or 900 mg ravulizumab will be administered (according to weight category) and on Day 15 patients will receive 900 mg of ravulizumab.

. If a patient is discharged before the end of the Primary Evaluation Period (Day 29), the patient will undergo the early discharge assessments. In addition, the patient will be contacted via telephone on Day 29 to assess health status (eg, survival, mechanical ventilation, hospitalization, intensive care unit, and dialysis). Follow-up telephone calls should be performed as planned unless the patient withdraws consent.

. The Early Termination Visit is to be conducted when the patient discontinues from the study during the Primary Evaluation Period. In addition, the patient will be contacted via telephone on Day 29 to assess health status (eg, survival, mechanical ventilation, hospitalization, intensive care unit, and dialysis).

. Additional monitoring will be performed during the 2 follow-up visits to review patient status, including survival and pregnancy, and to obtain information about new or worsening TESAEs. The follow-up will be conducted as a telephone call if the patient is discharged from the hospital or an in-person visit if the patient is still hospitalized.

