## 4. STUDY DESIGN

### 4.1. Overall Design

Study ALXN1210-COV-305 is a multicenter Phase 3, open-label, randomized, controlled study designed to evaluate the safety and efficacy of intravenous (IV) ravulizumab + BSC, compared with BSC alone, in patients with a confirmed diagnosis of SARS-CoV-2 infection, and a clinical presentation consistent with COVID-19 severe pneumonia, acute lung injury, or ARDS. Patients at least 18 years of age, weighing  $\geq 40$  kg, and admitted to a designated hospital facility for treatment will be screened for eligibility in this study. Accounting for a 10% nonevaluable rate, approximately 270 patients will be randomized in a 2:1 ratio (180 patients to receive ravulizumab + BSC, 90 patients to receive BSC alone).

Patients randomized to ravulizumab + BSC will receive a weight-based dose of ravulizumab on Day 1 (Table s1). On Day 5 and Day 10, doses of 600 mg or 900 mg ravulizumab will be administered (according to weight category) and on Day 15 patients will receive 900 mg ravulizumab. Patients in both treatment groups will continue to receive medications, therapies, and interventions per standard hospital treatment protocols for the duration of the study.

The study consists of a Screening Period of up to 3 days, a Primary Evaluation Period of 4 weeks, a final assessment at Day 29, and a Follow-up Period of 8 weeks. The 2 follow-up visits will be conducted 4 weeks apart as a telephone call if the patient is discharged from the hospital or an in-person visit if the patient is still hospitalized. The total duration of each patient’s participation is anticipated to be approximately 3 months (Figure 1).

Screening and the Day 1 visits can occur on the same day if the patient has met all inclusion and no exclusion criteria.

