
Duration of study
	
 
○ The Primary Evaluation Period was chosen in consideration of the critical status of patients who are admitted to the ICU due to COVID-19 associated lung injury and typical duration of their stay in the ICU.
 
○ A Follow-up Period, consisting of 2 follow-up visits conducted approximately 4 weeks apart on Day 60 and Day 90, will be implemented to determine survival, monitor for pregnancy, and obtain information about new or worsening TESAEs. This duration is appropriate given the clinical presentation of COVID-19 patients with lung injury.
 

Primary endpoint of survival (all-cause mortality) at Day 29
	
 
○ The mortality rate of patients with COVID-19 associated severe pneumonia, acute lung injury, or ARDS is staggeringly high (upwards of 50%). Often patients die within a very short time from initial onset of symptoms.
 
○ The chosen primary endpoint is anticipated to reflect a ravulizumab treatment effect over 4 weeks and thus an immediate impact on survival.
 

Secondary endpoints
	
 
○ Most secondary endpoints were selected based on Society of Critical Care Medicine recommendations for standardized endpoints in clinical studies using an intervention to reduce the duration of mechanical ventilation (Blackwood, 2019).
 
○ The SOFA score is a validated endpoint used in the critical care setting to determine clinical outcomes (eg, multiorgan failure) (Lambden, 2019).
 

Abbreviations: aHUS = atypical hemolytic uremic syndrome; ARDS = acute respiratory distress syndrome; BSC = best supportive care; COVID-19 = Coronavirus Disease 2019; ICU = intensive care unit; PD = pharmacodynamic; PK = pharmacokinetic; SARS = severe acute respiratory syndrome; SARS-CoV-2 = severe acute respiratory syndrome coronavirus 2; SOFA = sequential organ failure assessment; TESAЕ = treatment-emergent serious adverse event.

[figure not shown]

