7. STATISTICAL ANALYSIS

This study is a multicenter Phase 3, open-label, randomized, controlled trial designed to evaluate the safety and efficacy of IV ravulizumab + BSC, compared with BSC alone in patients with a confirmed diagnosis of SARS-CoV-2 infection, and a clinical presentation consistent with COVID-19 severe pneumonia, acute lung injury, or ARDS. The primary endpoint is survival (based on all-cause mortality) at Day 29.

An interim analysis for efficacy and futility is planned when approximately 50% of patients have completed Day 29. If the stopping criteria are met, the study may be terminated early for efficacy or futility depending on which stopping boundary is crossed. The early stopping boundaries for efficacy and futility (non-binding) will be constructed using an α -spending function as Lan-DeMets (O'Brien-Fleming) and a β -spending function as Gamma(-4), respectively.

Provided the study is not stopped early for efficacy or futility, the final primary analysis will be conducted when all patients have completed the Primary Evaluation Period, which is Day 29 (or early termination [ET]). This analysis will include all efficacy, safety, and available PK/PD/immunogenicity study data for regulatory submission purposes. This analysis will not be considered an interim analysis. A final analysis will be conducted when all participants have completed the study follow-up visits (or ET).

Day 1 will be defined as the date of the first infusion of ravulizumab for patients randomized and dosed with ravulizumab and as the later of the date of randomization or the date of Day 1 visit for patients randomized but not dosed with ravulizumab.

For this SAP, the randomization stratification factor refers to two strata based on endotracheal intubation status on Day 1: intubated or not intubated.

Summary statistics will be computed and displayed by treatment group and visit, where applicable. Descriptive statistics for continuous variables will include the number of patients, mean, standard deviation, median, minimum, and maximum. For categorical variables, frequencies, and percentages will be presented. Graphical displays will be provided as appropriate. Statistical analyses, other than for the primary analysis, will be performed based on a 2-sided Type I error of 5%.

Analyses will be performed using the Statistical Analysis Software (SAS®) Version 9.4 or higher.

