Changes in SpO₂/FiO₂ will be also be analyzed using a REML-based repeated measures approach (i.e. MMRM, [Mallinckrodt, 2008](#)) and all available longitudinal data. The model will include fixed effects for baseline SpO₂/FiO₂, age, randomization stratification factor, treatment group indicator, study day (Day 5, 10, 15, 22, 29), and study day by treatment group interaction. An unstructured covariance structure will be used to model the within patient errors. If this analysis fails to converge, the following structures will be tested and the final covariance structure will be determined by Akaike's information criterion (AIC): first-order autoregressive, compound symmetry, and Toeplitz. The Kenward-Roger approximation will be used to estimate denominator degrees of freedom. The daily post-baseline SpO₂/FiO₂ scores will be mapped to study day as described in [Appendix 9.4.6](#). For patients who die, remaining values up to Day 29 will be imputed as a score of 0, the worst possible value.

A sensitivity analysis will be performed using a control-based MNAR mechanism for the missing data as described for change from baseline in SOFA score at Day 29.

This analysis will be repeated for changes in PaO₂/FiO₂, where available, as a sensitivity analysis.

7.2.2.5. Duration of Hospitalization at Day 29

Duration of hospitalization at Day 29 will be analyzed in a similar manner as duration of ICU stay (ie, the number of days alive and not hospitalized). Missing data will be handled as described for number of days free of mechanical ventilation at Day 29. The proportion of patients discharged from the hospital will also be summarized and compared between the 2 treatment groups in a similar manner as the primary analysis of the primary endpoint.

7.2.2.6. Survival at Day 60 and Day 90

Survival (based on all-cause mortality) at Day 60 and Day 90 will be estimated using the KM method and compared using a log-rank test stratified by intubated or not intubated on Day 1. Hazard ratio and risk reduction will be summarized from a Cox proportional hazards model stratified by intubated or not intubated on Day 1. Confidence intervals (95%) will be presented for the survival estimates at Day 60 and Day 90 based on the complementary log-log transformation. KM curves for both treatment groups will be produced.

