9.5. Additional details on Statistical Methods

9.5.1. Time to Death, Censoring Time, and Calculations

For the primary analysis, only deaths up to Day 29 will be considered, where time to death \leq 29 days.

For the KM sensitivity analysis of the primary endpoint, a censoring indicator will be equal to 1 if the patient did not die (was censored), and 0 if the patient died on or before 29 days.

For patients who die during the Primary Analysis Period, the time to event (in days) is defined as:

$$\text{Time to Death} = (\text{Date of Death} - \text{Date of Day 1} + 1)$$

For patients who do not die during the Primary Analysis Period, the censoring time (in days) is defined as:

$$\text{Censoring Time} = \min(29 \text{ days}, \text{time on study})$$

where time on study is Disposition Date – Date of Day 1 +1 for patients who have left the study before 29 days or Data Cutoff Date (when the last patient has the Day 29 visit) – Date of Day 1 + 1.

For the secondary endpoint of survival at Day 60 and Day 90, the following will be used:

For patients who die during the Analysis Period, the time to event (in days) is defined as:

$$\text{Time to Death} = (\text{Date of Death} - \text{Date of Day 1} + 1)$$

For patients who do not die during the Analysis Period, the censoring time (in days) is defined as:

$$\text{Censoring Time} = (\text{EOAP Date} - \text{Date of Day 1} + 1)$$

where End of Analysis Period (EOAP) Date is the minimum non-missing value of the following dates: the Data Cutoff Date (when the last patient has the Day 29 visit) and the Final Disposition Date for patients who have left the study before the data cutoff date. Deaths observed after the EOAP date will not be included in the analysis.

These derivations will be repeated with the data cutoff date defined as when the last patient has completed the study.

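### At the primary cutoff, SAP 9.5.1 censors patients still in follow-up for Day 60/90 survival at the cutoff date, with no planned check that they are alive

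*SAP*

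**What the plan says.** SAP section 7 fixes the timing of the first analysis: "the final primary analysis will be conducted when all patients have completed the Primary Evaluation Period, which is Day 29" (or early termination). It is made for regulatory submission and includes all efficacy data.

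SAP section 7.2.2.6 gives the method for the later survival endpoint: "Survival (based on all-cause mortality) at Day 60 and Day 90 will be estimated using the KM method and compared using a log-rank test", with a stratified Cox model alongside.

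SAP section 9.5.1 defines the censoring. Patients who do not die are censored at the End of Analysis Period (EOAP) date, the minimum non-missing value of "the Data Cutoff Date (when the last patient has the Day 29 visit) and the Final Disposition Date for patients who have left" (that is, early leavers). It adds: "Deaths observed after the EOAP date will not be included in the analysis". It then provides for a second run: "These derivations will be repeated with the data cutoff date defined as when the last patient has completed the study".

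Protocol Table 4 describes the contacts after Day 29 as a follow-up period "consisting of 2 follow-up visits conducted approximately 4 weeks apart on Day 60 and Day 90, will be implemented to determine survival", among other purposes. Table 1 gives a ±7-day window. On the mode of contact, Table 1 footnote 5 says: "The follow-up will be conducted as a telephone call if the patient is discharged from the hospital". Patients still in hospital are seen in person.

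Neither document defines a last-known-alive date or schedules a survival check at the data cutoff.

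**The concern.** A Kaplan-Meier estimate is sound when a patient counted as at risk on a given day would have been recorded as dead had he or she died that day. For a discharged patient between two calls, that is not assured here. The rule credits the patient with survival up to the cutoff, although the last scheduled contact may be a month earlier. A death at home in that gap may not be known when the data are cut.

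The sentence on deaths observed after the EOAP date adds to the difficulty. It may mean deaths that occurred after that date, or deaths learned of after it. On the second reading, a death before the cutoff that surfaces at the next call is dropped, while the patient's time up to the cutoff is kept as survival.

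At stake are the Day 60 and Day 90 survival estimates, the log-rank test and the hazard ratio in the first report, which is the one made for submission.

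**Working it through.** **Plan's own figures.** No number in the plan depends on this rule. The design figures reproduce and are not in question: 243/(1 − 0.10) = 270, and O'Brien-Fleming-type spending at 50% information gives a final one-sided p of 0.0245.

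**Inputs from the documents.** Cutoff at the last patient's Day 29 visit (SAP 9.5.1). Contacts at Days 60 and 90 (Protocol Tables 1 and 4). Day 29 survival of 60% and 80% (SAP 9.3).

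**Assumptions, not in the documents.** Uniform accrual over A days, so study day at cutoff, f, is uniform on 29 to 29 + A. Constant hazard λ after Day 29, with 5% or 15% of Day 29 survivors dead by Day 90. Contacts on their nominal days. In the adverse case, every post-Day-29 death is learned of only at the next call.

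**Step 1, single patients.** On study day 55 at cutoff, last contacted on Day 29: 55 − 29 = 26 unverified days. On day 85, last contacted on Day 60: 85 − 60 = 25. The gap can reach 60 − 29 = 31 days before visit windows.

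**Step 2, how much follow-up is unverified.** Counted time is min(f, 90) − 29. Verified time is 0, 31 or 61 days for f below 60, from 60 to below 90, and 90 or more. For A = 90:
- Mean verified = 31 × 30/90 + 61 × 29/90 = 29.99 days
- Mean counted = 61²/(2 × 90) + 61 × 29/90 = 40.33 days
- Unverified share = 1 − 29.99/40.33 = 26%

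The same formula gives 50%, 17%, 10% and 7% for A = 60, 120, 180 and 240.

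**Step 3, effect on Kaplan-Meier.** Let G(t) be the proportion with f > t. In the adverse case a death between Days 29 and 60 is seen only if f ≥ 60, but everyone with f > t is in the risk set. The estimated hazard is then about λ·G(60)/G(t), and λ·G(90)/G(t) between Days 60 and 90. Integrating:
- A = 90: 59·ln(90/59) + 29·ln(59/29) = 24.9 + 20.6 = 45.5 effective days instead of 61, a ratio of 0.746
- A = 180: 149·ln(180/149) + 119·ln(149/119) = 28.2 + 26.8 = 54.9 (unrounded sum), a ratio of 0.900

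Estimated Day 90 survival among Day 29 survivors is the true survival raised to that ratio:

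| A (days) | Late mortality | True | Estimated | Excess (points) |
|---|---|---|---|---|
| 90 | 5% | 95.0% | 96.2% | 1.2 |
| 90 | 15% | 85.0% | 88.6% | 3.6 |
| 180 | 5% | 95.0% | 95.5% | 0.5 |
| 180 | 15% | 85.0% | 86.4% | 1.4 |

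Simulation of the same cases gave about 0.4 to 3.7 points. The largest is slightly above the approximation because patients with unreported deaths also stay in the risk set.

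Among all randomized patients the excess is smaller. At A = 90 with 15% late mortality, a simulated trial of 270 gave 71.4% against a true 68.5% for ravulizumab + BSC (2.9 points) and 52.8% against 50.8% for BSC alone (2.0 points).

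**Step 4, deaths known at once.** The estimated hazard becomes λ·G(t)/G(t) = λ, so cutoff censoring is unbiased.

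**Step 5, person-day shares against mortality.** For A = 60, nobody has passed study day 89 at the cutoff and no Day 90 call has been made. The effective time is 29·ln(60/29) = 21.1 days. Mortality is understated by about 1 − 21.1/31 = 32% at Day 60 and 1 − 21.1/60 = 65% at Day 89, against a person-day share of 50%. The share bounds neither.

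**Step 6, last-known-alive censoring alone.** Suppose deaths are reported at once but alive status only at calls. Deaths then come from all patients with f > t, while the risk set holds essentially those who reached the next call. The hazard is about λ·G(t)/G(60), then λ·G(t)/G(90). For A = 90:
- (90² − 59²)/(2 × 59) + (59² − 29²)/(2 × 29) = 39.1 + 45.5 = 84.7 effective days (unrounded sum), a ratio of 1.388
- 0.85^1.388 = 79.8%, against a true 85.0% (80.3% by simulation)

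**Step 7, cutting deaths and censoring at the last scheduled contact reached.** Deaths and risk set then come from the same patients, so the hazard is λ·G(60)/G(60) = λ, and likewise after Day 60. This is unbiased whether or not deaths are reported between calls.

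**The case against.** The strongest reply is that the plan largely deals with this already. The derivation is rerun when the last patient completes the study, by which time ongoing patients have reached Day 90 or have a disposition date. Day 60/90 survival sits outside the closed testing procedure (SAP 7.2.2). The rationale for Protocol Amendment 3 says that information on it may be insufficient at the Day 29 analysis. The Day 29 Kaplan-Meier analysis caps censoring at 29 days, and discharged patients get a Day 29 call. All of this stands and limits the importance of the point. It does not repair the Day 60/90 estimates still produced at the first cutoff.

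The second reply is that the bias is conditional. Patients in hospital are under observation, and sites must report serious adverse events within 24 hours of awareness (Protocol 8.6.1). This also stands: with prompt knowledge of deaths there is no bias. The documents do not say how a site would learn of a death at home between calls, nor how long after the cutoff the database is locked.

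A reader might take the 50% to 7% shares in Step 2 as upper limits on how far mortality is understated. They are not (Step 5). They describe follow-up without scheduled confirmation and nothing more.

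A reader might also infer that the treatment comparison is distorted. The rule is the same in both arms, and no distortion of the log-rank test or hazard ratio has been quantified. Its effect on the comparison would depend on late mortality by arm, which the documents do not give.

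**Conclusion.** The point holds for the first Day 60/90 survival estimate only. SAP 9.5.1 counts days as survival that no scheduled contact has confirmed. If deaths after discharge surface only at calls, the Day 90 estimate among Day 29 survivors is too high by about 0.4 to 3.7 points in each arm, under assumed accrual of 90 to 180 days and late mortality of 5% to 15%. If deaths are known at once, the bias is zero. The truth probably lies between, and the documents do not allow it to be placed.

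The documents do not support reading this as a threat to the primary result: the Day 29 endpoint, the ranked secondary endpoints and the type I error do not depend on the rule. Nor is it a lasting error in Day 60/90 survival, since the study-end rerun largely removes it. What can remain there is a disposition date later than the last contact for a patient lost to follow-up. The change is worth making because the first run goes into a submission and the repair is small.

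**What to change.** In SAP 9.5.1, require a vital-status check, by call or hospital record, of all ongoing patients at the primary cutoff. Censor at the confirmed date and count every death dated on or before it. Reword the sentence on deaths after the EOAP date so that it refers to the date of death, not the date the death was learned of.

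If the check is not done, use one of two alternatives:
- Cut both deaths and censoring at each patient's last scheduled survival contact reached by the cutoff (Day 29, 60 or 90).
- Report Day 60/90 survival only from the study-end cutoff.

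Do not switch to last-known-alive censoring alone. It biases survival downward when deaths are reported between calls and alive status is not (Step 6).

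The check costs one round of calls. The first alternative costs slightly less follow-up at the first cutoff, and the second delays the estimate to the end of the study.

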#### **8.4.12. Early Termination**

If a patient is discontinued from the study during the Primary Evaluation Period (ie, from Day 1 through Day 29), the patient should present for the Early Termination visit, to be conducted as specified in the SoA ([Table 1](#)). The patient will be contacted via telephone on Day 29 to assess health status (eg, survival, mechanical ventilation, hospitalization, intensive care unit, and dialysis).

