## 9. STATISTICAL CONSIDERATIONS

### 9.1. Statistical Hypotheses

The primary null hypothesis is that there is no difference in survival between ravulizumab + BSC and BSC alone as measured by the difference in the proportions surviving at Day 29 between the 2 treatment groups. The alternative hypothesis is that ravulizumab + BSC will improve survival at Day 29 compared with BSC alone.

The null hypotheses associated with the secondary objectives are that ravulizumab + BSC is no different than BSC alone for the respective endpoints; the alternative hypotheses are described below:

1. Number of days free of mechanical ventilation: The alternative hypothesis is that treatment with ravulizumab + BSC will increase the number days free of mechanical ventilation at Day 29 compared with BSC alone.
2. Duration of ICU stay: The alternative hypothesis is that treatment with ravulizumab + BSC will reduce the number days in the ICU at Day 29 compared with BSC alone.
3. Change in SOFA score: The alternative hypothesis is that treatment with ravulizumab + BSC will improve changes in SOFA score at Day 29 compared with BSC alone.
4. Change in SpO2/FiO2: The alternative hypothesis is that treatment with ravulizumab + BSC will improve changes in SpO2/FiO2 at Day 29 compared with BSC alone.
5. Duration of hospitalization: The alternative hypothesis is that treatment with ravulizumab + BSC will reduce the number days in the hospital at Day 29 compared with BSC alone.
6. Survival (based on all-cause mortality) at Day 60 and Day 90: The alternative hypothesis is that ravulizumab + BSC will improve survival at Day 60 and Day 90 compared with BSC alone.

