### 9.2. Sample Size Determination

A sample size of 243 patients (162 ravulizumab + BSC, 81 BSC alone) is required to ensure at least 90% power and detect an improvement in survival from 60% in the BSC alone group to 80% in the ravulizumab + BSC group at Day 29.

This sample size calculation assumes:

- 1-sided Z-test of the difference in 2 proportions,
- Type I error = 0.025,
- Pooled variance,
- 2:1 randomization on the 2 treatment groups,

- One interim analysis at 50% information which will be after collecting primary efficacy data on approximately 122 patients. The early stopping boundaries for efficacy and futility (nonbinding) will be constructed using  $\alpha$ -spending function as Lan-DeMets spending function with O’Brien-Fleming flavor and  $\beta$ -spending function as Gamma(-4) (Lan, 1983; Hwang, 1990).

Considering a nonevaluable rate of 10%, this study is planned to randomize approximately 270 patients (180 ravulizumab + BSC, 90 BSC alone).

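### SAP 9.5.1 censors patients who leave before Day 29 by two conflicting rules, and the Day 29 rule biases the time-to-event sensitivity analyses of survival downward

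*SAP*

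**What the plan says.** **Follow-up.** A patient who discontinues from the study during the Primary Evaluation Period has an Early Termination visit, and Protocol 8.4.12 adds: "The patient will be contacted via telephone on Day 29 to assess health status". Footnote 4 of the Schedule of Activities says the same. For patients discharged from hospital, footnote 3 goes further: "Follow-up telephone calls should be performed as planned unless the patient withdraws consent". Footnote 4 has no matching sentence.

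**Objective.** Protocol 9.1 states as an alternative hypothesis that "ravulizumab + BSC will improve survival at Day 60 and Day 90 compared with BSC alone". Efficacy is analysed in all randomised patients (Protocol 9.3, SAP 6.1).

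**Day 29 time-to-event rule (SAP 9.5.1).** A patient who dies on or before 29 days is an event at the date of death. A patient who does not die is censored at the smaller of 29 days and time on study. Time on study runs to the disposition date "for patients who have left the study before 29 days or Data Cutoff Date" otherwise.

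**Day 60/90 rule (same section).** The analysis period ends at the earlier of the data cutoff and the final disposition date of a patient who has left. Then: "Deaths observed after the EOAP date will not be included in the analysis". The repeat at the end of the study moves the data cutoff only.

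**Primary analysis.** SAP 9.5.1 limits it to deaths up to Day 29 and sets no cut at disposition. Missing status is multiply imputed (SAP 7.2.1.1).

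**The concern.** Kaplan-Meier, log-rank and Cox methods need censoring that does not depend on what happens to the patient afterwards. Under the Day 29 rule, two patients who leave on the same day and are both traced by the Day 29 call are treated differently according to the answer. The one who died stays in the risk set until death. The one who lived is removed from the day of leaving. Deaths are kept in full while the survivors' person-time is discarded, so estimated survival must fall.

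The Day 60/90 rule treats leavers who die and leavers who live alike, so it does not have this fault. It does discard known outcomes. A death on Day 20 learned from the call counts in the Day 29 proportion and the Day 29 curve but is absent from the Day 60/90 curve, so the two curves can disagree at Day 29 on the same data.

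At stake are the time-to-event sensitivity analyses of the primary endpoint (SAP 7.2.1: stratified log-rank, stratified Cox, adjusted Cox) and the Day 60/90 survival endpoint.

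**Working it through.** **The plan's own figures.** Protocol 9.2 sizes the trial with a "1-sided Z-test of the difference in 2 proportions", "Type I error = 0.025", pooled variance, 2:1 allocation and Day 29 survival of 60% versus 80%. The pooled proportion is (0.6 + 2×0.8)/3 = 0.7333. The control-arm size is [1.960·√(0.7333×0.2667×1.5) + 1.2816·√(0.6×0.4 + 0.8×0.2/2)]² / 0.2² = (1.0615 + 0.7250)²/0.04 = 79.8, so 80, and 240 in total for a fixed design. The plan's 243 with one interim look agrees, and 243/0.9 = 270. The 60% and 80% are therefore used as true Day 29 survival below.

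**Assumptions not in the documents.** The exit rate *q* (3%, 5% or 10%; 10% is borrowed from the nonevaluable rate, which is not a withdrawal rate), constant hazard to Day 29, and vital status at Day 29 known for every leaver.

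**Day 29 rule, all exits on Day 5, unrelated to prognosis.** Let S be true Day 29 survival and p = S/S^(5/29) the survival from Day 5 to Day 29. After Day 5 the risk set contains everyone still alive except the leavers who will survive, so with S(t) as survival since Day 5 its size is proportional to S(t) − qp. Deaths are all retained. The Kaplan-Meier factor from Day 5 to Day 29 is then (p − qp)/(1 − qp), and the estimate is

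S × (1 − q)/(1 − qp).

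- BSC, S = 0.60: p = 0.6552. At q = 0.10: 0.60×0.90/(1 − 0.06552) = 0.5779.
- Ravulizumab, S = 0.80: p = 0.8314. At q = 0.10: 0.80×0.90/(1 − 0.08314) = 0.7853.

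With exits spread evenly over Days 1 to 28, the same calculation day by day gives smaller errors:

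| Exit rate | Day 5 exits, BSC / rav | Spread exits, BSC / rav |
|---|---|---|
| 3% | 59.4% / 79.6% | 59.6% / 79.75% |
| 5% | 58.9% / 79.3% | 59.3% / 79.6% |
| 10% | 57.8% / 78.5% | 58.6% / 79.1% |

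The truth is 60% / 80% throughout. The error runs from 80 − 79.75 = 0.25 (about 0.3) to 60 − 57.8 = 2.2 points per arm. It is larger in the arm with higher mortality, so equal exit rates widen the apparent difference slightly. At 10% it is 78.5 − 57.8 = 20.7 points with Day 5 exits, or 79.1 − 58.6 = 20.5 with spread exits, against a true 20.0. If leavers found alive are censored at Day 29 instead, nobody is censored early and the estimate equals the true proportion.

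**Day 60/90 rule.** This was simulated with 400,000 patients per arm and 10% exits spread over Days 1 to 28, assuming Day 90 survival of 55% / 75% among patients who stay.

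- Deaths by Day 29 after exit are 1.83% of BSC and 0.98% of ravulizumab patients: 90×0.0183 + 180×0.0098 = 3.4 known deaths dropped, out of 90×0.4 + 180×0.2 = 72 expected.
- Exit unrelated to prognosis: the Day 90 estimate is 55.0% / 75.0%, equal to the truth.
- Hazard doubled after exit: estimate 55.0% / 75.0%, truth 53.5% / 73.8% (too high).
- Hazard one quarter after exit: estimate 54.9% / 75.1%, truth 56.6% / 76.2% (too low).

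**The case against.** The case against giving this much weight is substantial, and most of it stands.

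- **The primary result is safe.** A reader might infer that the plan wastes the Day 29 call. It does not. The primary analysis is a stratified proportion with no disposition-date cut, missing status is imputed, and SAP 7.2.1.1 lists six missing-data sensitivity analyses. The Day 29 rule touches only sensitivity analyses, and Day 60/90 survival is outside the closed testing procedure (Protocol 9.4.1.3, SAP 7.2.2).
- **The Day 60/90 rule is ordinary censoring at exit.** A reader might infer that it overstates survival. That needs leavers to do worse; if they do better, the sign reverses.
- **Size.** A reader might infer a bias of 1.5 to 3 points in the treatment difference. That requires Day 5 exits, leaving confined to one arm and, at the top end, 20% leaving. Protocol 7.2 expects withdrawal to be uncommon, and under 7.1 patients who only stop study drug remain in the study.
- **Late contact.** That leavers are called only on Day 29 is inferred from silence and the contrast with footnote 3. Footnote 5 describes survival review at both follow-up visits without excluding them.
- **A careless repair can recreate the fault.** Counting every death whenever reported, while censoring unreached survivors early, is again asymmetric. With 10% leaving, half unreached and all deaths learned (assumed), a true Day 90 survival of 50.0% is estimated as 49.0%.

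What remains is that the Day 29 rule as written gives a wrong answer even under random leaving. One escape is to read the undefined Primary Analysis Period as ending at each patient's exit, but the censoring indicator in SAP 9.5.1 is defined by death on or before 29 days, without that condition.

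**Conclusion.** The point holds in limited form. SAP 9.5.1 applies outcome-dependent censoring in the Day 29 time-to-event sensitivity analyses. This lowers estimated survival by about 0.3 to 2.2 points per arm for assumed exit rates of 3% to 10%, with constant hazard and full tracing at Day 29. With similar exit rates in both arms, the effect on the difference is well under one point. If leaving were confined to one arm, that arm's error would pass straight into the difference, but nothing in the documents says this will happen.

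The Day 60/90 rule drops deaths that the Day 29 analyses count. Its certain cost is lost information and two curves that can disagree at Day 29; bias requires informative exit and has no fixed direction. The wording mismatch is certain. Its size is not, because the documents give no exit rate.

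**What to change.** **SAP 9.5.1: one rule for both analyses.**

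- For a leaver whose vital status is obtained at a scheduled contact, count a death by its date and censor a survivor at that contact date, capped at Day 29, 60 or 90 as applicable.
- For a leaver whose status is not obtained at a scheduled contact, end follow-up for deaths and survivors alike at the last scheduled contact where status was obtained, or at disposition if there was none. Deaths that surface later then do not restore the asymmetry.
- Reword the EOAP sentence so that it applies only to the administrative data cutoff, not to the disposition date. It should not be deleted, because the cutoff still needs it.

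**Protocol footnote 4 and Section 8.4.12.** State that vital status is also sought on Day 60 and Day 90 for patients who discontinued, unless consent to contact is withdrawn, in line with footnote 3 for discharged patients.

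**Cost.** The SAP change is wording only. The protocol change means up to two calls per leaver and an amendment with IRB/IEC approval (Protocol 10.1.1). Alpha and sample size do not change.
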